5.1.2.6 Injection Volume

The total injection volume will be 3.0 - 4.0 mL depending on the size of the prostate.

5.1.2.7 Intraprostatic Injection Procedure

Subjects will be seen as outpatients the day of the adenovirus injection. The injection procedure will be performed in a private treatment room with restricted access. Biosafety Level 2 procedures will be followed throughout.

Adenovirus injections will be performed transrectally under transrectal ultrasound guidance (TRUS) typically using 20 gauge needles. The subject will be placed in the left lateral decubitus position with the legs flexed and the knees brought up toward the chest. The buttocks are placed over the edge of the examining table to allow for the appropriate manipulation of the ultrasound probe. Prior to the adenovirus injection, the subject will receive a local injection of 1% lidocaine into the area surrounding the prostatic capsule. Two needle passes (one medial, one lateral) will be made in the left and right sides of the prostate starting at the base and proceeding toward the apex until all of the adenovirus is delivered.

Used syringes and needles will be disposed of properly. After the procedure, the treatment room will be cleaned with an approved disinfectant.

5.1.2.8 **Toxicity**

Injection procedure- Possible side effects of the injection procedure include infection, gross hematuria and urinary retention. Infection occurs in less than 1% of cases. Antibiotic therapy will be given as prophylaxis prior to and after the adenovirus injection. Gross hematuria following prostate biopsy occurs in less than 1% of cases and is usually self-limited. Injection of the adenovirus into the prostate may cause local swelling that could lead to acute urinary retention. A Foley catheter will be placed, if needed.

Ad5-*yCD/mutTK_{SR39}rep-hIL12* adenovirus- Based on the results of five phase 1/2 trials with similar oncolytic adenoviruses lacking IL-12 (36-44), likely adverse events attributable to the oncolytic adenovirus include transient flu-like symptoms (37 of 79 subjects or 47%) and transaminitis (32 of 79 subjects or 41%). The vast majority (> 94%) of these events were mild (grade 1) to moderate (grade 2). The flu-like symptoms typically resolve within a few days and can be alleviated with analgesics. The transaminitis is self-limiting and typically resolves within 2 weeks.

The toxicities associated with IL-12 administration are well-established (59, 62, 63), some of which overlap those associated with the adenovirus and prodrug therapy. It is possible/likely that IL-12 will exacerbate flu-like symptoms (e.g., chills/rigor, fever, malaise), hepatic toxicity (e.g., transaminitis, ALKP, bilirubin), and hematological events (e.g., anemia, leukopenia, lymphopenia, neutropenia, thrombocytopenia). Other adverse events possibly/probably related to IL-12 administration include: ascites, confusion, capillary leak syndrome, cytokine release syndrome, dehydration, delirium, diarrhea, dizziness, dyspnea, edema, headache, hypotension, nausea, pleural effusion,

tachycardia, and vomiting.

5.1.2.9 Dose Modification

Subjects will receive only a single adenovirus injection. No dose modifications are necessary.

5.1.3 Prodrug Therapy

5.1.3.1 Description

5-fluorocytosine (5-FC, Ancobon[®]) is approved for the treatment of serious infections caused by susceptible strains of *Candida* and *Cryptococcus*. Valganciclovir (vGCV, Valcyte[®]) is approved for the treatment of CMV retinitis in people with AIDS.

5.1.3.2 Supply of 5-FC and vGCV Prodrugs

Both 5-FC (Ancobon[®]) and vGCV (Valcyte[®]) are commercially available. 5-FC (Ancobon[®]) is manufactured by Valeant Pharmaceuticals and is available as 250 and 500 mg capsules for oral administration. vGCV (Valcyte[®]) is manufactured by Hoffman La-Roche and is available as 450 mg tablets for oral administration.

5.1.3.3 Storage of 5-FC and vGCV Prodrugs

5-FC (Ancobon[®]) and vGCV (Valcyte[®]) should be stored as directed by the supplier.

5.1.3.4 Duration of Prodrug Therapy

All subjects will receive a one week (7 day) course of 5-FC (Ancobon[®]) + vGCV (Valcyte[®]) prodrug therapy beginning two days after the adenovirus injection (**Figure 5**).

5.1.3.5 5-Fluorocytosine (5-FC, Ancobon[®]) Dose

The 5-FC (Ancobon[®]) dosage will be 150 mg/kg per day given in four equally divided doses. Due to 5-FC (Ancobon[®]) only being available in 250 and 500 mg capsules, the dose may be rounded up or down to the nearest possible amount. The capsules will be taken a few at a time over a 15 minute period.

5.1.3.6 Valganciclovir (vGCV, Valcyte[®]) Dose

The vGCV (Valcyte[®]) dosage will be 1,800 mg/day given twice daily (2 x 450 mg tablets per dose) with food.

5.1.3.7 Toxicity

The most common side effects associated with 5-FC (Ancobon[®]) + vGCV (Valcyte[®]) prodrug therapy include neutropenia and thrombocytopenia. In five previous phase 1/2 trials representing 79 subjects (36-44), 19 of 79 (24%) subjects exhibited grade 1 - 3 neutropenia and 26 of 79 (33%) subjects exhibited grade 1/2 thrombocytopenia. The prodrugs may also contribute to anemia (32 of 79 subjects or 41%) and possibly lymphopenia (69 of 79 subjects or 87%). Except for lymphopenia, the vast majority of these events are mild (grade 1) to moderate (grade 2). Sixty-four percent (64%) of the events of lymphopenia were moderate (grade 2) and 25% were severe (grade 3). All hematologic events are transient and self-limiting, and typically resolve within two (anemia, neutropenia, thrombocytopenia) to six (lymphopenia) weeks.

Other possible side effects associated with 5-FC (Ancobon[®]) + vGCV (Valcyte[®]) prodrug therapy include nausea, vomiting, diarrhea and headache.

5.1.3.8 Dose Modifications

5-FC and vGCV doses will be modified based on the guidelines below.

5.1.3.8.1 Cytopenia

5.1.3.8.1.1 Absolute neutrophil count < 1,000/ μ L or platelet count < 100,000/ μ L- reduce 5-FC and vGCV doses to 75%.

5.1.3.8.1.2 Absolute neutrophil count < 500/ μ L or platelet count < 50,000/ μ L- discontinue 5-FC and vGCV, and resume the drugs at 50% of the original dose when the neutrophil count is > 500/ μ L and platelets > 50,000/ μ L.

5.1.3.8.2 Creatinine Clearance

If creatinine clearance (CrCl) is < 50 mL/min/m², follow the guidelines in **Table 6** and check the creatinine every other day (except weekends). Creatinine clearance should be calculated based on the most recent creatinine level as follows:

$$\text{CrCl} = \frac{(\text{140} - \text{age [years]}) \times (\text{body weight [kg]})}{(\text{72}) \times (\text{serum creatinine [mg/dL]})}$$

Table 6. Ancobon and Valcyte Dose Modifications

Creatinine Clearance	Ancobon	Valcyte
≥ 50	No modifications	No modifications
≥ 40 and < 50	Reduce to 75 mg/kg/day	Reduce to 450 mg b.i.d.
≥ 25 and < 40	Reduce to 37.5 mg/kg/day	Reduce to 450 mg q.d.
< 25	Suspend	Suspend

In all cases, if creatinine clearance improves, Ancobon and Valcyte doses can be increased (resumed) once according to guidelines in **Table 6**. If creatinine clearance drops a second time, Ancobon and Valcyte dosage should be reduced accordingly, but may not be increased if creatinine clearance improves. In all cases, the subject should take no more than a maximum of 7 days of prodrug medication (regardless of the dose received). If prodrugs are suspended continuously for > 2 weeks, the subject should not receive any further prodrugs.

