3.2.4 Age ≥ 18 years

- 3.2.5** Karnofsky performance status ≥ 70 .
- 3.2.6** Negative lymph nodes as established by imaging (pelvic CT or pelvic MRI) within 90 days of registration.
 - 3.2.6.1** Subjects with lymph nodes equivocal or questionable by imaging are eligible if the nodes are ≤ 1.0 cm.
 - 3.2.6.2** Subjects with positive lymph nodes by capromab pentetide (ProstaScint) scans are eligible provided a corresponding lymph node identified by CT or MR imaging is ≤ 1.0 cm.
- 3.2.7** No evidence of metastatic disease, as evaluated by bone scan and CT scan of the abdomen and pelvis within 90 days prior to registration. Equivocal bone scan findings are allowed if plain films are negative for metastasis.
- 3.2.8** Subjects must have adequate baseline organ function, as assessed by the following laboratory values, within 30 days before initiating the study therapy:
 - 3.2.8.1** Adequate renal function with serum creatinine ≤ 1.5 mg/dL or creatinine clearance >50 mL/min/m².
 - 3.2.8.2** Platelet count $> 100,000/\mu\text{L}$.
 - 3.2.8.3** Absolute neutrophil count $> 1,000/\mu\text{L}$.
 - 3.2.8.4** Hemoglobin > 10.0 g/dL.
 - 3.2.8.5** Bilirubin < 1.5 mg/dL
 - 3.2.8.6** AST/SGOT and ALT/SGPT < 3.0 times upper limit of normal (ULN).
- 3.2.9** Men of child-producing potential must be willing to consent to use effective contraception for at least 3 months after the gene therapy.
- 3.2.10** Subjects must possess the ability to give informed consent and express a willingness to meet all of the expected requirements of the protocol for the duration of the study.

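### The renal cut-off is printed per m² but the formula has no surface-area term, and eligibility on creatinine alone admits men whom Table 6 already places on a reduced prodrug row

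*Combined protocol and SAP*

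**What the plan says.** Eligibility criterion 3.2.8.1 reads "Adequate renal function with serum creatinine ≤ 1.5 mg/dL or creatinine clearance >50 mL/min/m²". The two limbs are alternatives, and no formula is given there.

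Section 5.1.3.8.2 opens its dose-modification rule with "If creatinine clearance (CrCl) is < 50 mL/min/m²". It then gives the method: "Creatinine clearance should be calculated based on the most recent creatinine level as follows". The formula is (140 − age) × weight in kg, divided by 72 × serum creatinine in mg/dL. Table 6 bands the result at 50, 40 and 25 without a unit. From 40 to below 50 the 5-FC entry is "Reduce to 75 mg/kg/day"; from 25 to below 40 it is "Reduce to 37.5 mg/kg/day"; below 25 both prodrugs are suspended.

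The unmodified 5-FC "dosage will be 150 mg/kg per day given in four equally divided doses" (5.1.3.5), and unmodified vGCV is 1,800 mg/day (5.1.3.6). Section 5.1.3.8 makes both subject to the modification guidelines.

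Section 6.3.2.4 defines the MTD by adenovirus dose. Section 6.3.2.3 counts toxicity related to the study treatment as a whole.

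**The concern.** There are two separate problems.

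First, an operative threshold is stated in a unit that its own formula cannot produce. Without height or surface area, the formula cannot give a figure per m². The unit appears in two sections, so it does not look like a single slip. In 3.2.8.1 it is the only guide, because no formula is printed there. A reader who takes the unit literally must add a division that the protocol never describes, and may reach a different prodrug row or a different eligibility decision.

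Second, the 'or' in 3.2.8.1 lets a man qualify on creatinine alone. Some such men have a formula value below 50 before their first prodrug dose, so Table 6 starts them on a reduced row. Section 5.1.3.4 and Figure 5 describe one prodrug course for all subjects.

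The primary objective is touched because prodrug toxicity can count as DLT. Section 5.1.3.7 names neutropenia and thrombocytopenia as the commonest prodrug effects. Section 6.3.2.3 exempts grade 3 neutropenia only if it reverses within 72 hours, and gives thrombocytopenia no exemption. No section sets a minimum prodrug dose for a subject to count in the escalation decision. In a cohort of three, one man on a reduced row is a third of the evidence.

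**Working it through.** The plan states no worked figure here, so there is none to reproduce. The printed formula is evaluated directly.

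**Inputs from the protocol.** Clearance = (140 − age) × kg / (72 × creatinine); cut-offs 50, 40 and 25; 5-FC 150, 75 and 37.5 mg/kg/day; creatinine limit 1.5 mg/dL.

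**Assumptions, not in the documents.** Patient age, weight, height and creatinine; surface area = √(cm × kg / 3600), with a range of 1.7 to 2.2 m².

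**1. Size of the unit gap.** A cut-off of 50 per m² corresponds to a formula value of 50 × surface area: 50 × 1.7 = 85 and 50 × 2.2 = 110. Read literally, it is 1.7 to 2.2 times stricter than a formula value of 50.

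**2. Effect on a Table 6 row.** Age 70, 85 kg, creatinine 1.0:
- Formula: 70 × 85 / 72 = 82.6, no modification.
- At 175 cm: surface area √(175 × 85 / 3600) = 2.03; 82.6 / 2.03 = 40.7 per m², the 75 mg/kg/day row (75/150 = half).
- At 165 cm: 82.6 / 1.97 = 41.9, the same row. At 185 cm: 82.6 / 2.09 = 39.5, the 37.5 mg/kg/day row (a quarter).
- Over the whole assumed range: 82.6 / 1.7 = 48.6 to 82.6 / 2.2 = 37.6, always in a reduced row.

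**3. Effect on eligibility.** This arises only for men with creatinine above 1.5, who need the clearance limb. Age 60, 100 kg, 175 cm, creatinine 1.8: 80 × 100 / (72 × 1.8) = 61.7, eligible. Surface area √(175 × 100 / 3600) = 2.20; 61.7 / 2.20 = 28.0 per m², not eligible.

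**4. The 'or', using the bare formula only.** At creatinine 1.5 the formula is below 50 when weight is below 50 × 72 × 1.5 / (140 − age) = 5400 / (140 − age):

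| Age | Weight below which the formula gives < 50 |
|---|---|
| 60 | 67.5 kg |
| 65 | 72.0 kg |
| 70 | 77.1 kg |
| 75 | 83.1 kg |
| 80 | 90.0 kg |

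Examples at creatinine 1.5, all meeting 3.2.8.1:
- Age 75, 80 kg: 65 × 80 / 108 = 48.1, half-dose row.
- Age 78, 70 kg: 62 × 70 / 108 = 40.2, half-dose row.
- Age 80, 65 kg: 60 × 65 / 108 = 36.1, quarter-dose row.

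**5. Illustrative grid.** Ages 60 to 80 by 1 year, weights 65 to 110 kg by 5, creatinine 0.8 to 1.5 by 0.1, height 175 cm: 21 × 10 × 8 = 1,680 combinations. The formula value is below 50 in 137 (8%). The per-m² value is below 50 in 1,502 (89%), and the Table 6 row differs between the two readings in the same number. These are counts of combinations, not patient frequencies.

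**The case against.** The strongest reply is that the protocol tells staff how to calculate clearance and Table 6 lists plain numbers. Formula in, row out: each man has one dose, and no section asks for division by surface area. The grid supports this. The literal unit would put most combinations on a reduced row, which fits poorly with 150 mg/kg/day and 1,800 mg/day as the planned doses. This stands. A reader might infer that the prodrug dose tested is undetermined; the documents do not support that. A reader might also infer that one man could receive full, half or quarter dose according to the unit. Two readings give one man at most two rows.

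The second reply is that the 'or' is a design choice. Criterion 3.2.8.1 does not promise that every entrant has clearance above 50, and 5.1.3.8 provides for modified doses. This also stands: the 'or' leaves no dose undefined. What remains is that nothing says whether starting on a reduced row was foreseen, and the escalation rule takes no account of it.

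Third, the examples in step 4 sit at the creatinine limit, and the row depends on the most recent creatinine, which may differ from the screening value. Agreed. Nor does a lower dose at lower clearance by itself show lower systemic exposure; the protocol plans no prodrug levels that would settle this.

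Finally, Table 10 already lists a Prodrug Therapy form, so no data-capture gap is shown. The gap is in the planned reporting: section 8.3 promises descriptive toxicity results without mention of prodrug dose received.

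**Conclusion.** The renal threshold in 3.2.8.1 and 5.1.3.8.2 is wrong as written, because its unit and the only printed formula cannot both apply. Followed by formula, each man gets one Table 6 row. Followed by unit, the cut-off is 1.7 to 2.2 times stricter for surface areas of 1.7 to 2.2 m²; it can move a man to a reduced row and can reverse eligibility for those relying on the clearance limb. The contradiction in the text is certain; the sizes rest on assumed patient values and an assumed surface-area equation.

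Separately, and whatever the unit, creatinine-only eligibility admits some men whose formula value is already below 50. Prodrug dose can then vary within a cohort while the MTD refers to adenovirus dose alone. The documents give no basis for saying how often. A reader might infer that the MTD would be invalid; the documents show only that it could rest on mixed prodrug doses that the planned report would not make visible.

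**What to change.** - Reconcile the unit in 3.2.8.1 and 5.1.3.8.2 with the formula, and print the same unit in Table 6. Whether the unit or the calculation changes is for the clinical team. If the eligibility checklist has a renal item (the pages before item 10 were not available for this review), check that it agrees.
- Have the clinical team confirm whether the 'or' in 3.2.8.1 is intended alongside Table 6. If it is not, the two sections must be reconciled; if it is, say so in the text.
- From the existing Prodrug Therapy form, list prodrug dose received beside DLTs at each adenovirus dose level, and mark subjects who started on a reduced row.

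The cost is a wording amendment, one derived variable and one extra descriptive listing. No additional subjects are needed. With 3 to 6 men per cohort the listing supports no formal comparison, but it shows which prodrug doses each escalation decision rested on.

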5.1.4 Other Medications

5.1.4.1 Antibiotics

To reduce the risk of infection, subjects will be given ciprofloxacin (500 mg, p.o., b.i.d.) the evening before, and the morning of, the adenovirus injection, continuing the antibiotic twice daily for a total of 3 days. They will also receive gentamicin (120 mg, I.M.) just prior to the adenovirus injection. If the subject is allergic to ciprofloxacin, another antibiotic can be substituted at the discretion of the treating physician.

6.0 SUBJECT ASSESSMENTS

Subject assessments are summarized in **Table 7**.

Table 7. Subject Assessments

Parameters	Pre-Study Therapy	First 2 Weeks	Follow Up
History, Physical Examination, DRE	X ^a		X ⁱ
EPIC and EQ-5D Instruments	X ^a		X ⁱ
Bone Scan	X ^a		X ^k
CT Scan	X ^a		X ^k
On-site Physician Assessment	X ^b	X ^e	X ⁱ
Hematology (CBC/DP)	X ^b	X ^f	X ⁱ
Blood Chemistries	X ^b	X ^f	X ⁱ
Urinalysis	X ^b		
Diagnostic Serum PSA	X ^b	X ^e	X ⁱ
Toxicity Assessment	X ^b	X ^f	X ⁱ
Molecular Studies	X ^b	X ^g	X ^f
IL-12 and IFN- γ ELISA	X ^b	X ^g	X ^f
NK Cytolytic Assay	X ^b	X ^h	
Chest Radiographs	X ^c		
TRUS-Guided Needle Biopsy	X ^d		
Pathology Assessment	X ^d		

^aWithin 90 days of registration. ^bWithin 30 days of registration. ^cWithin 90 days of registration if the subject has history of pulmonary disease; otherwise, within 180 days. ^dWithin 180 days of registration. ^eOnce a week for the first two weeks. ^fTwice a week for the first 2 weeks. ^gAt every blood draw until not detected in two consecutive measurements. ^hAt every blood draw during the first two weeks. ⁱAt every scheduled follow-up visit at 1, 3, 6, 9, 12, 18, 24 months and then annually thereafter. ^jAt 6, 12, and 24 months. ^kIn subjects who experience bone pain or at PSA relapse and then annually thereafter.

6.1 Assessments During First Two Weeks After Adenovirus Injection

The following assessments will be performed:

- 6.1.1 An on-site physician assessment will be performed once a week.
- 6.1.2 CBC/DP and blood chemistries will be measured twice a week, or as clinically indicated.
- 6.1.3 Diagnostic serum PSA.
- 6.1.4 Ad5- γ CD/*mutTK_{SR39}rep-hIL12* viral DNA in blood will be measured at every scheduled blood draw until not detected in two consecutive measurements.
- 6.1.5 Serum IL-12 and IFN- γ will be measured at every scheduled blood draw until not detected in two consecutive measurements.
- 6.1.6 NK cytolytic activity will be measured at every scheduled blood draw during the first two weeks after the adenovirus injection.
- 6.1.7 Toxicity assessments will be performed twice a week using protocol-specific Case Report Forms (CRFs). Toxicity assessments will be based on physical examinations, diagnostic evaluations, and laboratory tests.

6.2 Assessments Following the Study Therapy

Follow-up visits will occur at 1, 3, 6, 9, 12, 18 and 24 months after the adenovirus injection and then at least annually thereafter. Evaluations will include:

- 6.2.1** History and physical examination including DRE.
- 6.2.2** CBC/DP and blood chemistries.
- 6.2.3** Diagnostic serum PSA.
- 6.2.4** EPIC and EQ-5D instruments at 6, 12, and 24 months.
- 6.2.5** Ad5-*yCD/mutTK_{SR39}/rep*-hIL12 viral DNA in blood will be measured at every scheduled blood draw until not detected in two consecutive measurements.
- 6.2.6** Serum IL-12 and IFN- γ will be measured at every scheduled blood draw until not detected in two consecutive measurements.
- 6.2.7** A bone scan will be performed on any subject with complaints of bone pain that cannot be attributed to any intercurrent disease. Discretionary plain films and/or MRI may be needed to evaluate lesions seen on bone scan to confirm the diagnosis of metastatic disease.
- 6.2.8** In subjects with biochemical failure, a bone scan and CT scan of the abdomen and pelvis should be performed at that time and then annually and/or as clinically indicated.
- 6.2.9** Toxicity assessments will be performed at every scheduled follow-up visit using CRFs specifically designed for this trial. Toxicity assessments will be based on physical examinations, diagnostic evaluations, and laboratory test results.
- 6.2.10** It is understood that the performance of an individual study or test as specified in this protocol is subject to factors such as subject compliance, schedule difficulties, equipment malfunction, or the judgment of the principal investigator or patient care physicians, and that a test may not be done in an individual instance without violating the protocol. However, any systematic modification of the original protocol in this regard, whether related to subject safety or not, will be submitted to the IRB for approval.

6.3. Toxicity Assessments

6.3.1 Adverse Event Grading Criteria

Adverse events will be graded according to NCI's Common Terminology Criteria for Adverse Events (CTCAE) v4.03 (68). Adverse events will be documented using CRFs specifically designed for this trial.

6.3.2 Definitions

6.3.2.1 Definition of Adverse Event (AE)

An adverse event is defined as any undesirable experience associated with the use of a medical product (69). Adverse events will be categorized as depicted in **Table 8** (70).

Table 8. Categorization of Adverse Events		
Relationship	Attribution	Description
Unrelated to investigational agent/intervention	Unrelated	The AE is clearly NOT related to agent/intervention
	Unlikely	The AE is doubtfully related to agent/intervention
Related to investigational agent/intervention	Possible	The AE may be related to agent/intervention
	Probably	The AE is likely related to agent/intervention
	Definite	The AE is clearly related to agent/intervention

6.3.2.2 Definition of Serious Adverse Event (SAE)

A SAE is defined as any undesirable experience associated with the use of a medical product that results in any of the following outcomes:

6.3.2.2.1 Death.

6.3.2.2.2 A life-threatening experience.

6.3.2.2.3 Hospitalization or prolongation of existing hospitalization.

6.3.2.2.4 Disability or permanent damage.

6.3.2.2.5 A congenital anomaly/birth defect.

6.3.2.2.6 Required intervention to prevent permanent impairment or damage.

6.3.2.2.7 Other serious events that may jeopardize the subject and may require medical or surgical intervention (treatment) to prevent one of the other outcomes.

6.3.2.3 Definition of Dose-Limiting Toxicity (DLT)

Dose-limiting toxicity is defined as any of the following adverse events considered possibly/probably/definitely related to the study treatment.

6.3.2.3.1 \geq Grade 2 allergic reaction or generalized urticaria.

6.3.2.3.2 \geq Grade 2 cardiovascular or neurologic toxicity.

6.3.2.3.3 \geq Grade 3 hematologic or non-hematologic toxicity of any duration except for:

6.3.2.3.3.1 Grade 3 lymphopenia with recovery within 2 weeks.

6.3.2.3.3.2 Grade 3 anemia, leukopenia, or neutropenia that is reversible within 72 hours.

6.3.2.3.3.3 Grade 3/4 fever or flu-like symptoms that are reversible within 72 hours.

6.3.2.3.3.4 Grade 3 SGOT/SGPT that is reversible within 72 hours.

6.3.2.3.3.5 Grade 3 hyperglycemia that can be explained by patient's baseline comorbidity (i.e., diabetes).

6.3.2.3.3.6 Grade 3 hypermagnesemia that is reversible within 72 hours.

6.3.2.3.3.7 Grade 3 hypophosphatemia that is reversible within 72 hours.

